10.2.1 Exposure duration

The duration of each AE will be calculated as follows:

$$\text{Duration (days)} = \text{Date of outcome} - \text{Date of onset} + 1 \quad (40)$$

For the calculation of duration for AEs with missing start dates, the dates will be imputed as described in Section 4.2.2.

The time to first dose for each AE will be calculated as follows for all TEAEs:

$$\begin{aligned} \text{Time since first dose (days)} \\ = \text{Date of AE onset} - \text{Date of first dose} + 1 \end{aligned} \quad (41)$$

The time to most recent dose for each AE will be calculated as follows for all TEAEs:

$$\begin{aligned} \text{Time since most recent dose (days)} \\ = \text{Date of AE onset} \\ - \text{Date of most recent dose prior to AE} + 1 \end{aligned} \quad (42)$$

Time to first dose and time to most recent dose will not be calculated for pretreatment AEs.

For the calculation of time to first bimekizumab and time to most recent bimekizumab dose the same formulas as above (41 and 42) will be used but the date of first bimekizumab dose will be used instead of the date of first dose. The time to first dose and time to first bimekizumab dose differs only for those subjects who receive placebo at Baseline.

10.2.2 Exposure adjusted incidence rate (EAIR) and exposure adjusted event rate (EAER)

The EAIR is defined as the number of subjects (n_{AE}) with a specific AE adjusted for the exposure and will be scaled to 100 patient-years:

$$EAIR = 100 * \frac{n_{AE}}{\sum_{i=1}^{n_{AE}} T_{Exp,i} + \sum_{j=1}^{n_{noAE}} T_{Risk,j}} \quad (43)$$

where $T_{Exp,i}$ is a subject's exposure time in years up to the first occurrence of the AE of interest (equation [40] in years) at the level of coding evaluated, n_{noAE} the number of subjects without the specific AE and $T_{Risk,j}$ the total time at risk scaled to 100 patient-years (Section 10.1).

If a subject has multiple events at the level of coding evaluated, the time of exposure is calculated to the first occurrence of the AE of interest. If a subject has no events, the total time at risk (Section 10.1) in years is used. As indicated above, exposure-adjusted incidence rates will only be calculated for the overall treatment period. These presentations do not include AEs that occur under Placebo treatment. Therefore, a subject's exposure time will only start at the first dose of bimekizumab in the Dose-Blind Period for subjects randomized to Placebo at Baseline. Also, for subject's randomized to bimekizumab 16mg at Baseline, exposure time will only be

considered from the start of Dose-Blind Period, when presenting AEs for the bimekizumab 160mg and bimekizumab 160mg with loading dose, or bimekizumab 320mg groups. All exposure time on any bimekizumab dose is considered for the all bimekizumab column.

Exact Poisson 95% CIs for incidence rates are calculated using the relationship between the Poisson and the Chi-square distribution (Ulm, 1990; Fay and Feuer, 1997):

$$LCL = \frac{\chi_{2n, \frac{\alpha}{2}}^2}{2} \quad (44)$$

$$UCL = \frac{\chi_{2(n+1), 1-\alpha/2}^2}{2} \quad (45)$$

$$CI_{Lower} = 100 * \frac{LCL}{\sum_{i=1}^{n_{AE}} T_{Exp,i} + \sum_{j=1}^{n_{noAE}} T_{Risk,j}} \quad (46)$$

$$CI_{Upper} = 100 * \frac{UCL}{\sum_{i=1}^{n_{AE}} T_{Exp,i} + \sum_{j=1}^{n_{noAE}} T_{Risk,j}} \quad (47)$$

where n_{AE} is the number of subjects with a specific AE for the incidence rate of interest and is the basis for the number of the degrees of freedom for the chi-square quantile for the upper tail probability χ^2 , $T_{Exp,i}$ is a subject's exposure time in years up to the first occurrence of the AE of interest (equation [40] in years) at the level of coding evaluated, n_{noAE} the number of subjects without the specific AE and $T_{Risk,j}$ the total time at risk scaled to 100 patient-years (Section 10.1).

The EAER will be the number of AEs including repeat occurrences in individual subjects divided by the total time at risk scaled to 100 patient-years and calculated using:

$$EAER = 100 * \frac{N_{AE}}{\sum_{j=1}^{n_{All}} T_{Risk,j}} \quad (48)$$

where N_{AE} is the total number of AEs, $T_{Risk,j}$ is a subject's total time at risk in years and n_{All} the number of subjects.

No CI will be computed for EAER.

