- If first treatment allocation visit date is missing then the all activities events will be assumed to be treatment emergent.

Imputation of Partial Stop Dates:

- If only the month and year are specified, then use the last day of the month,
- If only the year is specified, then use December 31st of that year.
- If the stop date is completely unknown, do not impute the stop date.

In the event of ambiguity or incomplete data which makes it impossible to determine whether the AE was treatment emergent, the AE will be considered treatment emergent.

If the intensity of an AE is unknown, it is considered as severe.

If the relationship to study drug is missing, it is considered as related.

The imputation rule for missing seriousness differ between the interim and final analysis. For the interim analysis no imputations rule will be applied. For the final analysis the worst case approach will be applied. If the seriousness of an AE is missing for the final analysis, it is considered as serious.

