12.2 Calculation rules for duration of adverse events

The calculation rules for duration of AEs are presented in [Table 12–2](#). AE duration is computed and reported in day.

Table 12–2: Calculation rules for duration of adverse events

Data Availability	Onset Date	Outcome Date	Calculation Rules
Complete data	D1	D2	Duration = D2 – D1 + 1

Table 12–2: Calculation rules for duration of adverse events

Data Availability	Onset Date	Outcome Date	Calculation Rules
Start date missing	-	D2	Duration = < D2 – D0 + 1 Where, for a subject in the SS, D0 is the date of the first intake of IMP, and for screen failures, D0 is the date of the Screening visit day
End date missing	D1	-	Duration => Final contact date – D1 + 1 For resolved and ongoing AE Duration
Start and end date missing	-	-	Duration => Final contact date – D0 + 1 For resolved and ongoing AE Duration Where, for subjects in the SS, D0 is the date of the first intake of IMP, and for screen failures, D0 is the date of the Screening visit day

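### SAP 10.2.2 describes T_Exp as exposure up to the first AE but cites equation (40), which is the duration of the AE; a program built from the citation would give wrong EAIRs and confidence intervals.

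*SAP*

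**What the plan says.** SAP 10.2.2 defines the EAIR (equation 43) as 100 times the number of subjects with the AE, divided by the sum of T_Exp over affected subjects plus T_Risk over unaffected subjects. T_Exp is described as "exposure time in years up to the first occurrence of the AE of interest (equation [40] in years". The same description and citation appear again where the confidence limits (equations 46 and 47) are explained.

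Equation (40) is in SAP 10.2.1, introduced by "The duration of each AE will be calculated as follows". It is outcome date minus onset date plus 1. Equation (41), directly below it, is AE onset minus first dose plus 1. A bimekizumab version uses the first bimekizumab dose instead, and the SAP says of it: "The time to first dose and time to first bimekizumab dose differs only for those subjects who receive placebo at Baseline".

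Section 10.2.2 also says where exposure time starts. For subjects randomized to placebo it starts at their first bimekizumab dose in the Dose-Blind Period. For the other switching group, "for subject's randomized to bimekizumab 16mg at Baseline, exposure time will only be" counted from the start of the Dose-Blind Period in the 160mg and 320mg columns.

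**The concern.** The description and the cited formula are different quantities. The description measures time before onset, from the start of exposure. Equation (40) measures time after onset. A subject with onset on day 100 and outcome on day 106 has T_Exp of 100 days by the description and 106 - 100 + 1 = 7 days by equation (40).

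The citation is easy to follow by mistake. Equation (40) is the first formula under a heading that reads Exposure duration, and the wrong number is given twice.

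Equation (40) also has no definite value for some AEs. Section 4.2.2 states "If the stop date is completely unknown, do not impute the stop date", and for a missing end date Table 12-2 gives only an open-ended bound, "Duration => Final contact date" minus onset plus 1.

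At stake are the EAIRs and their intervals for the complete treatment period: all TEAEs, serious TEAEs, TEAEs leading to discontinuation, adverse drug reactions and the safety-topic tables listed in SAP 10.2.

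**Working it through.** The documents give no numerical EAIR, so there is no figure to reproduce. The check compares the two definitions at the planned trial size.

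**Inputs from the SAP.** There are 40 subjects per arm (2.4), and placebo and 16mg subjects are rerandomized 1:1 to 160mg or 320mg at Week 12 (2.3). For subjects who enter the extension study, T_Risk is Week 48 minus first injection plus 1 (equation 30), which is 48 × 7 + 1 = 337 days. For ex-placebo subjects it runs from the first Dose-Blind injection (equation 34), which is 36 × 7 + 1 = 253 days.

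**Assumptions.** All subjects complete and enter the extension. Incidence is equal across groups, and 365.25 days make a year. Incidence, onset day and AE duration are illustrative values, not document figures.

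**Formulas.** PT = [sum of T_Exp over affected + sum of T_Risk over unaffected] / 365.25, and EAIR = 100 × n / PT. The limits are 100 × [chi-square(0.025; 2n) / 2] / PT and 100 × [chi-square(0.975; 2(n+1)) / 2] / PT.

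**All-bimekizumab column** (160 subjects at 337 days, 40 at 253 days). Worked case with 80% affected, so n = 160:

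- Unaffected time: 32 × 337 + 8 × 253 = 12,808 days.
- By the description, onset day 45: (160 × 45 + 12,808) / 365.25 = 54.8 years, EAIR 292.
- By equation (40), duration 14 days: (160 × 14 + 12,808) / 365.25 = 41.2 years, EAIR 388.

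| Affected | Onset day | AE duration (days) | EAIR by description (95% CI) | EAIR by equation (40) (95% CI) | Change |
|---|---|---|---|---|---|
| 80% | 45 | 14 | 292 (249-341) | 388 (331-453) | +33% |
| 80% | 45 | 60 | 292 (249-341) | 261 (222-304) | -11% |
| 45% | 100 | 10 | 74 (60-91) | 91 (73-112) | +22% |
| 10% | 120 | 14 | 12.2 (7.4-18.8) | 12.6 (7.7-19.5) | +4% |
| 10% | 120 | 200 | 12.2 (7.4-18.8) | 11.9 (7.2-18.3) | -3% |
| 2% | 120 | 14 | 2.31 | 2.33 | under 1% |
| 2% | 120 | 200 | 2.31 | 2.30 | under 1% |

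**320mg column** (40 + 20 + 20 = 80 subjects). Mean T_Risk is (40 × 337 + 40 × 253) / 80 = 295 days. With 60 subjects affected, onset on day 90 and 7-day AEs, the EAIR goes from 193.9 (148.0-249.6) to 346.8 (264.6-446.3). Over onset days 30 to 150 and durations 7 to 180 days, the ratio of the equation (40) result to the description result runs from 0.46 to 2.36 with 60 affected. With 1 affected it runs from 0.994 to 1.006. With none affected nothing changes.

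**Would citing equation (41) be enough?** No. Its bimekizumab version moves the clock only for placebo subjects, so 16mg subjects would be counted from Baseline, 84 days too early for the 160mg and 320mg columns. Take 30% incidence and onset 60 days after the column start:

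- 160mg column (80 at 337 days, 40 at 253 days; n = 36, of whom 6 are ex-16mg). Unaffected time is 56 × 337 + 28 × 253 = 25,956 days. Affected time is 36 × 60 = 2,160 days, or 2,160 + 6 × 84 = 2,664 days. The EAIR goes from 46.8 to 45.9, -1.8%.
- 320mg column (40 at 337 days, 40 at 253 days; n = 24, of whom 6 are ex-16mg). Unaffected time is 28 × 337 + 28 × 253 = 16,520 days. Affected time is 24 × 60 = 1,440 days, or 1,944 days. The EAIR goes from 48.8 to 47.5, -2.7%.

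**The case against.** The best reply is that this is only a wrong cross-reference. Section 10.2.2 describes the right quantity, repeats that exposure runs to the first occurrence, and gives start rules that make no sense for an AE's duration. A careful programmer would see that equation (40) contains no dose date and set it aside. No stated figure is wrong, the program is not in the documents, and the large shifts need very common rows and assumed onset and duration. Several of the planned EAIR tables are for specific events; if these are uncommon, the effect there is negligible. The EAIR is descriptive, and the crude incidence and the EAER beside it would still be correct. The caution about equation (41) concerns a repair the SAP does not propose.

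Most of that stands as a limit on the point. The intent is recoverable, the harm is conditional, and no efficacy result is touched. It does not remove the mismatch: nothing in the current SAP corrects the citation. The Amendment 5 log shows the AE-duration formula and the citation both moving from 21 to 40, so the last renumbering kept the citation on AE duration. The equation (41) caution adds no weight to the error, but it matters for wording the correction, because changing 40 to 41 is the obvious quick repair.

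**Conclusion.** The concern holds. T_Exp is described one way and referenced another, and equations (43), (46) and (47) all depend on it. If the reference is programmed, short AEs push the EAIR and its interval up and long AEs push them down. For common rows such as all TEAEs the error can be tens of percent: +33% or -11% in the 80% example, and more in a single dose column. At 10% incidence it is about +4% or -3%, and at 2% it is under 1%. These sizes rest on assumed incidence, onset, duration and full completion. The EAER, rows with no affected subjects, the crude incidence tables for both periods and all efficacy analyses are unaffected. It should be fixed, but it does not threaten the trial's main conclusions.

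**What to change.** In both places in SAP 10.2.2, replace the reference to equation (40) with: date of first AE onset minus start of exposure for the column plus 1, in years (the form of equation 41). State the start of exposure as:

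- the first bimekizumab dose, for subjects randomized to placebo;
- the first Dose-Blind injection, for subjects randomized to 16mg when shown in the 160mg or 320mg column;
- the first injection, in all other cases.

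These are the start rules the section already sets. As a clean-up, remove the scaling to 100 patient-years from the definition of T_Risk: the section elsewhere gives T_Risk in years, and equation (43) already carries the factor 100.

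Then check the safety-table program against this definition. The cost is one wording change made twice, one clean-up and that check. No new data are needed.

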10.2.3 AE of Special Interest and AE of Special Monitoring

AE of special interest is any AE which meets the Hy's Law criteria, defined as $\geq 3x$ upper limit of normal (ULN) alanine aminotransferase (ALT) or aspartate aminotransferase (AST) with coexisting $\geq 2x$ ULN total bilirubin in the absence of $\geq 2x$ ULN alkaline phosphatase (ALP), with no alternative explanation for the biochemical abnormality.

AE of special monitoring for this study include:

- Infections (serious, opportunistic, fungal and TB)
- Malignancies, including lymphoma
- Major cardiovascular events
- Neutropenia
- Neuropsychiatric events (in particular depression and suicide)
- Inflammatory bowel disease
- Anaphylactic reaction
- Hepatic events

For the definitions of AE of special monitoring the Bimekizumab Safety Topics of Interest (Version date 19Feb2018) will be used.

The incidence of TEAEs of special monitoring will be summarized by MedDRA system organ class, high level term, and PT. EAIR with associated 95% CI and the EAER will be included in the summary tables. Serious infections are also classified as AE of special monitoring but no separate table will be produced.

The output table for the search criteria Standardized MedDRA Query (SMQ) = “Malignant or unspecified tumours (SMQ)” will include two different overall rows:

- The first overall incidence row will summarize “Any malignancies (including unspecified)” and this row will summarize the incidence of all AEs flagged for inclusion in the table, regardless of the High Level Term (HLT) it codes to.
- The second overall incidence row will summarize “Any malignancy (including unspecified, excluding non-melanomic skin cancers)” and this row will summarize the incidence of AEs flagged for inclusion in the table, excluding those which code to an HLT of “skin neoplasms malignant and unspecified (excl melanoma)”.

The output table for the search criteria SMQ=“Malignant tumours (SMQ)” will include two different overall rows:

- The first overall incidence row will summarize “Any malignancies” and this row will summarize the incidence of all AEs flagged for inclusion in the table, regardless of the High Level Term (HLT) it codes to.
- The second overall incidence row will summarize “Any malignancy (excluding non-melanomic skin cancers)” and this row will summarize the incidence of AEs flagged for inclusion in the table, excluding those which code to an HLT of “skin neoplasms malignant and unspecified (excl melanoma)”.

The output table for Anaphylactic reaction will include three different overall rows:

- The first row within the body of the table will be labeled “Any hypersensitivity/anaphylactic reaction” and will represent the overall incidence of subjects who reported at least one hypersensitivity reaction or at least one anaphylactic reaction.

- The second row within the body of the table will be labeled “Any hypersensitivity reaction” and will represent the overall incidence of subjects who reported at least one hypersensitivity reaction.
- The third row within the body of the table will be labeled “Any anaphylactic reaction” and will represent the overall incidence of subjects who reported at least one anaphylactic reaction.

10.3 Clinical laboratory evaluations

The routine clinical laboratory evaluations specified in [Table 10–1](#) and will be summarized. If any additional analytes are also recorded then these will be listed only.

Different summary tables for hematology and biochemistry variables will be provided, based on data from scheduled visits: observed values and change from Baseline, shift from Baseline to maximum post-Baseline value (in Double-Blind Period), shift from Baseline to maximum post-Baseline value (in Dose-Blind Period), shift from Baseline to minimum post-Baseline value (in Double-Blind Period), shift from Baseline to minimum post-Baseline value (in Dose-Blind Period), shift from Baseline to end of treatment (in Double-Blind Period), shift from Baseline to end of treatment (in Dose-Blind Period), and markedly abnormal laboratory data.

End of treatment (in Double-Blind Period) will be defined as the last visit in the Double-Blind Period or the early termination assessment depending if the subject discontinued in the Double-Blind Period.

End of treatment (in Dose-Blind Period) will be defined as the Week 48 visit or the early termination assessment depending if the subject discontinued early or not.

In addition, number of subjects who meet the Hy’s Law criteria ([Section 10.2](#)) will be described using the frequencies.

All laboratory data will be listed by treatment, subject and visit including changes from Baseline for numeric variables, flags for measurements outside the normal ranges, the relative study day, a flag for whether the test was not done and a flag for whether the subject was fasting.

Additional listings will be presented for Hepatitis B and C, human immunodeficiency virus (HIV), genomic proteomic/metabolomics, and genetic/epigenetic tests. C-reactive protein (CRP) and hs-CRP will be listed separately in the efficacy section.

Table 10–1: Laboratory measurements

Hematology	Biochemistry	Urinalysis
Basophils	Calcium	Bacteria
Eosinophils	Chloride	Crystals
Lymphocytes	Magnesium	Glucose
Monocytes	Potassium	pH
Neutrophils	Sodium	RBC
Hematocrit	Glucose	WBC

Table 10–1: Laboratory measurements

Hematology	Biochemistry	Urinalysis
Hemoglobin	BUN	Urine dipstick for pregnancy testing ^b
MCH	Creatinine	
MCHC	hs-CRP/CRP ^a	
MCV	AST	
Platelet count	ALT	
RBC count	GGT	
WBC count	ALP	
	Total bilirubin	
	LDH	
	Total cholesterol	
	Uric acid	
	Albumin	
	Serum pregnancy testing ^b	

ALP=alkaline phosphatase; ALT=alanine aminotransferase; AST=aspartate aminotransferase; BUN=blood urea nitrogen; CRP=C-reactive protein; GGT=gamma glutamyltransferase; hs-CRP=high sensitivity C-reactive protein; LDH=lactate dehydrogenase; MCH=mean corpuscular hemoglobin; MCHC=mean corpuscular hemoglobin concentration; MCV=mean corpuscular volume; RBC=red blood cell; SFU=Safety Follow-up; WBC=white blood cell

^a Both CRP and hs-CRP will be tested at specified visits per Protocol Table 5.1.

^b A serum pregnancy test will be performed at Screening for all women of childbearing potential. This recommendation also applies to women of childbearing potential with infrequent or irregular menstrual cycles and women during menopause. Natural menopause is recognized to have occurred after 12 consecutive months of amenorrhea, for which there is no other obvious pathological or physiological cause (International Menopause Society, 2015). A urine pregnancy test is also required at the Baseline, Week 48, ET, and at SFU visits. A urine pregnancy test will also be performed at any study visit where there has been a delay in menses. This recommendation also applies to women of childbearing potential with infrequent or irregular menstrual cycles. Pregnancy test results must be negative prior to administering IMP.

Markedly abnormal values for biochemistry and hematology will be defined as laboratory values graded 3 or 4 according to the Rheumatology Common Toxicity Criteria (RCTC). Definitions of the markedly abnormal values are given in Table 10–2 and Table 10–3 and are based on the RCTC units. All units in the tables below will be converted to the standard units based on Clinical Data Interchange Standards Consortium (CDISC) standards. The markedly abnormal laboratory results will be listed separately.

Values that are below the lower limit of the reference range will be flagged as ‘L’ (low) and values that are above the upper limit of the reference range will be flagged as ‘H’ (high) and listed as well.

For tables where data are summarized by visit, unscheduled and repeat visits will not be summarized, but these data will be included in listings. In the case where laboratory values are below the LLOQ, then these will be set to the midpoint between 0 and the LLOQ for the purpose of summarizing the data.

Table 10–2: Definitions of markedly abnormal hematology values

Variable (RCTC Units)	Markedly Abnormal Definition	
	Low	High
Hemoglobin (g/dL)	<LLN AND >2.0 decrease from Baseline	N/A
Hemoglobin (g/dL)	<8.0	N/A
Leukocytes (total x 1000)	<2.0	N/A
Lymphocytes (x 1000)	<0.5	N/A
Neutrophils (x 1000)	<1.0	N/A
Platelets (x 1000)	<50	N/A

LLN=lower limit of normal; N/A=not applicable; RCTC= Rheumatology Common Toxicity Criteria.

Table 10–3: Definitions of Markedly Abnormal Biochemistry Values

Variable (RCTC Units)	Markedly Abnormal Definition	
	Low	High
ALP	N/A	>3 x ULN
ALT	N/A	>3 x ULN
AST	N/A	>3 x ULN
Calcium (mg/dL)	<7.0	>12.5
Creatinine (mg/dL)	N/A	>1.8 x ULN
Glucose (mg/dL)	<40	>250
Potassium (mmol/L)	<3.0	>6.4
Sodium (mmol/L)	<125	N/A
Total bilirubin	N/A	≥2 x ULN
Uric acid	N/A	≥3 x ULN

ALP=alkaline phosphatase; AST=aspartate aminotransferase; N/A=Not applicable; RCTC= Rheumatology Common Toxicity Criteria; ULN=upper limit of normal

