### 12.5.1 Evaluation of PDILI

The PDILI IMP discontinuation criteria for this study are provided in Section 6.3.1, with the accompanying required follow-up investigation and monitoring detailed below. All PDILI events must be reported as an AE and reported to the study site and sponsor within 24 hours of learning of their occurrence. Any PDILI event that meets the criterion for potential Hy’s Law must be reported as an AE of special interest (see Section 12.1.2), and, if applicable, also reported as an SAE (see Section 12.2.1).

Evaluation of PDILI consists of the diagnostic testing and continued monitoring included in [Table 12–3](#) (specific tests dependent on laboratory results and corresponding symptoms) and consultation with a local hepatologist (if applicable; discussed in [Section 12.5.1.1](#)). The local hepatologist is the expert usually consulted by the treating physician for assessment and management of potential hepatic disease. This would usually be a hepatologist, but may be a gastroenterologist. Additional investigation and monitoring may be required and adapted based on the diagnosis after the cause of the liver injury/abnormality is confirmed (details in [Section 12.5.1.5](#)).

The results of all monitoring, including laboratory testing and other testing, should be made available to the study site and sponsor.

All initial tests resulting in abnormal hepatic laboratory values need to be repeated, but appropriate medical action must not be delayed waiting for the repeat result.

If tests are done locally for more rapid results, a concurrent sample should also be sent to the central laboratory whenever possible. Medical care decisions are to be made initially using the most rapidly available results and a conservative approach must be taken if the results from the 2 laboratory tests are significantly different. Data from the local and central laboratory are to be recorded on the applicable CRF pages.

When IMP is discontinued, all concomitant medications and herbal supplements that are not medically necessary should also be discontinued. In these cases, the Investigator should also consider dose reduction for medically necessary concomitant medication and consider changing any medically required concomitant medication known to be hepatotoxic to a suitable alternative.

Rechallenge with a substance potentially causing drug-induced liver injury is dangerous, may be fatal, and must not occur.

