**Table 12-3: Required investigations and follow-up for PDILI**

Laboratory value		Symptoms a of hepatitis of hypersensitivity	Immediate		Follow-up	
ALT or AST	Total bilirubin		Consultation requirements	Actions	Testing	Evaluation
≥3xULN	≥2xULN b	NA	Hepatology consult c Medical Monitor must be notified within 24 hours (eg, by laboratory alert) and subject discussed with Medical Monitor ASAP.	Immediate, permanent IMP discontinuation	Essential: Must have repeat liver chemistry values and additional testing completed ASAP (see Section 12.5.1.4); recommended to occur at the site with HCP.	Monitoring of liver chemistry values at least twice per week until values normalize, stabilize, or return to within baseline values d
≥3xULN	NA	Yes				
≥5xULN	NA	NA	Need for hepatology consult to be discussed. (required if ALT or AST ≥8xULN) Medical Monitor must be notified within 24 hours (eg, by laboratory alert) and subject discussed with Medical Monitor ASAP.	Immediate, permanent IMP discontinuation		
≥3xULN (and ≥2x baseline) and <5xULN (and ≥2x baseline)	<2xULN	No	Discussion with Medical Monitor required. Consider need for hepatology consult if there is no evidence of resolution (see	Further investigation – immediate IMP discontinuation not required (see Section 12.5.1.2). IMP discontinuation required if any of the	Essential: Every attempt must be made to have repeat liver chemistry values and additional testing completed within 48 hours at the site	Monitoring of liver chemistry values at least twice per week for 2 weeks. d • Immediate IMP discontinuation required if liver

This document cannot be used to support any application for marketing authorization therof.

REDACTED COPY

This document cannot be used to support any application for marketing authorization therof.

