3 DATA ANALYSIS CONSIDERATIONS

3.1 General presentation of summaries and analyses

All computations and generation of outputs will be performed using SAS® Version 9.3 or later. All tables and listing will use Courier New font size 9.

All original and derived variables will be listed and described using summary statistics (number of observations [n], mean, standard deviation [SD], median, minimum and maximum, unless otherwise stated) or frequency counts (number of subjects [N] and percentages). For multiple post-Baseline assessments at a specific visit, the first non-missing measurement will be used for summary statistics or frequency counts.

Descriptive statistics will be displayed to provide an overview of the study results. For categorical variables, the number and percentage of subjects in each category will be presented. The denominator for percentages will be based on the number of subjects appropriate for the purpose of analysis. Unless otherwise noted, all percentages will be displayed to 1 decimal place. No percentage will be displayed for zero counts, and no decimal will be presented when the percentage is 100%. For continuous variables, descriptive statistics will include number of subjects with available measurements (n), mean, SD, median, minimum, and maximum.

Decimal places for descriptive statistics will always apply the following rules:

- “n” will be an integer.
- Mean, SD, and median will use 1 additional decimal place compared to the original data.
- Coefficient of variance (CV[%]) will be presented with 1 decimal place.
- Minimum and maximum will have the same number of decimal places as the original value.

Statistical tests of efficacy variables will be presented as 2-sided p-values rounded to 3 decimal places. P-values less than 0.001 will be presented as “<0.001” and p-values greater than 0.999 will be presented as “>0.999” Statistical comparisons will be performed by two-sided statistical tests at the 0.050 level of significance.

The SAS output for Cochran-Mantel-Haenszel test, logistics regression, and analysis of covariance (ANCOVA), as well as multiple imputation (MI) will be provided as a separate PDF document in addition to TFLs. The SAS output will be included in the ‘Documentation of Statistical Methods’ section of the clinical study report.

In the Double-Blind Period the order of treatment groups will be presented in tables from left to right will be

- Placebo
- Bimekizumab 16mg
- Bimekizumab 160mg

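### SAP 10.3 limits the worst-value shift and markedly abnormal laboratory tables to scheduled visits, so liver values that first cross a threshold at protocol-required off-schedule tests are not tabulated

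*SAP*

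**What the plan says.** SAP 10.3 opens the description of the haematology and biochemistry tables with "Different summary tables for hematology and biochemistry variables will be provided, based on data from scheduled visits". The tables named after the colon include "shift from Baseline to maximum post-Baseline value (in Double-Blind Period", its Dose-Blind counterpart, the corresponding minimum shifts, the shifts to end of treatment, and, as the last item, "and markedly abnormal laboratory data".

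Further down, the same section has a second rule: "For tables where data are summarized by visit, unscheduled and repeat visits will not be summarized, but these data will be included in listings". SAP 3.1 adds a general rule: "For multiple post-Baseline assessments at a specific visit, the first non-missing measurement will be used for summary statistics or frequency counts". SAP 3.1 also puts repeat and unscheduled measurements into every listing. SAP 10.4 says that laboratory results from potential drug-induced liver injury (PDILI) work-ups are listed only.

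On the protocol side, section 12.5.1 states: "All initial tests resulting in abnormal hepatic laboratory values need to be repeated". For the categories that require permanent discontinuation of study drug, Table 12-3 asks for "Monitoring of liver chemistry values at least twice per week until values normalize, stabilize, or return to within baseline values". The milder category is monitored at least twice weekly for two weeks and then until resolution or stabilization. Protocol 6.3 asks for hepatic markers every week or every two weeks after withdrawal for a laboratory abnormality. Protocol 8.7 allows safety laboratory tests at unscheduled visits when medically indicated. Protocol 12.5 directs unscheduled samples to the central laboratory.

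**The concern.** Restricting by-visit summaries to scheduled visits is ordinary practice, because it keeps denominators comparable across visits. A maximum, a minimum or a count of threshold crossings has a different purpose: to show how bad the value became. Once a liver value is abnormal, the protocol moves follow-up between the scheduled visits, and under SAP 10.3 those results cannot enter the tables meant to show the worst value.

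At stake is the incidence by dose of markedly abnormal liver results and, to a lesser degree, blood counts. Neutropenia and hepatic events are adverse events of special monitoring in SAP 10.2.3, and this is a dose-ranging trial. Listings carry the individual values but do not give incidence by arm.

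**Working it through.** The plan states no figure here, so the check is a comparison of texts followed by cases.

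**Scope of the restriction.** The scheduled-visit phrase stands before the colon and governs the whole list. The maximum and minimum shifts and the markedly abnormal table are in that list. The later sentence in SAP 10.3 excludes unscheduled and repeat visits only where data are summarized by visit; read alone, it would leave the worst-value tables open to all values. The opening sentence closes them. SAP 13.4.2 shows that the phrase was added to that sentence by Amendment 4. No current section brings unscheduled or repeat values back into these tables. A repeat attached to the same visit is also dropped, by the first-non-missing rule in SAP 3.1.

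**Thresholds.** SAP Table 10-3: ALT, AST and ALP above 3 x ULN; total bilirubin at or above 2 x ULN. SAP Table 10-2: neutrophils below 1.0 and lymphocytes below 0.5 (x 1000).

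**Cases.**

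1. *Scheduled ALT between 1 x and 3 x ULN, repeat above 3 x ULN.* The scheduled value does not meet the table definition and the repeat is not used, so the subject is not counted as markedly abnormal.
2. *Scheduled ALT at or above 5 x ULN with bilirubin below 2 x ULN; bilirubin reaches 2 x ULN during twice-weekly monitoring.* The subject is counted for ALT but not for bilirubin.
3. *Scheduled ALT above 3 x ULN with a higher value on repeat.* The subject is already counted for ALT. The recorded maximum is not the peak. The SAP does not define the shift categories; if they follow the low/high reference-range flags in SAP 10.3, the shift cell does not change.
4. *Study drug stopped after Week 12 for a liver event.* Protocol 6.3 gives an Early Termination Visit and then a Safety Follow-up Visit 20 weeks after the last dose. SAP 3.5 maps the Early Termination values to a scheduled visit, so they are tabulated. The monitoring between the two visits is not.
5. *Neutrophils at or above 1.0 at scheduled visits and below 1.0 at an unscheduled visit.* The subject is not counted. Here the test is discretionary (Protocol 8.7), not mandated.

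The loss therefore falls on values that first cross a threshold off schedule (cases 1, 2 and 5, and case 4 where the crossing comes after the Early Termination Visit), not on higher peaks in subjects already counted (case 3).

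**The case against.** The strongest reply is that little is lost. Intensive monitoring starts at ALT or AST of 3 x ULN, next to the table threshold of more than 3 x ULN, so a subject whose monitoring began with a scheduled sample is usually already counted for that enzyme. Repeat and unscheduled values are in all listings, and markedly abnormal results have their own. Protocol 12.5.1 requires every PDILI event to be reported as an adverse event, and SAP 10.2 tabulates hepatic and cytopenia events with exposure-adjusted rates. All of this stands and limits the size of the problem. It does not give incidence of laboratory threshold crossings by arm. One could also read the repeat-test sentence, which sits in the PDILI section, as covering PDILI cases only. Case 1 would then largely fall away, but cases 2 and 4 would remain.

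Three stronger readings are tempting and are not supported:

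- *A size derived from visit spacing.* A reader might infer that, with 28 days between visits, an excursion of 7, 14 or 21 days is seen with probability 7/28, 14/28 or 21/28 (25%, 50%, 75%). That ignores the Week 1 and Week 2 samples. Double-Blind samples at Weeks 1, 2, 4, 8 and 12 leave gaps of 1, 1, 2, 4 and 4 weeks. With a uniform start over 12 weeks, the chance is the sum of min(length, gap) divided by 12: (1+1+1+1+1)/12 = 5/12, (1+1+2+2+2)/12 = 8/12 and (1+1+2+3+3)/12 = 10/12, or 42%, 67% and 83%. Only the Dose-Blind Period is 4-weekly throughout. More fundamentally, either set describes detection by scheduled sampling, not loss from excluding unscheduled results. An excursion that nobody samples leaves no value to recover.
- *Mandatory repeat blood counts.* The protocol's repeat and monitoring requirements cited here name hepatic values. Unscheduled blood counts are at the investigator's discretion.
- *A Hy's Law count limited to scheduled visits.* SAP 10.3 introduces that count separately, outside the scheduled-visit list. Its data source is simply not stated.

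**Conclusion.** The point holds for the tables named. As written, SAP 10.3 keeps off-schedule liver results that the protocol requires out of the maximum and minimum shift tables and the markedly abnormal table, and its two statements on unscheduled data do not agree in scope. It is worth correcting before the final tables are produced.

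The size cannot be estimated: neither document gives the number of repeat or unscheduled tests. The direction is clear, since adding values can only leave a maximum, a minimum or a crossing count unchanged or make it more extreme. The conclusion rests on reading the opening phrase as covering the whole list, which is its plain grammar, and on off-schedule central-laboratory results being available, as Protocol 12.5 provides. The primary and secondary efficacy analyses are not affected.

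**What to change.** In SAP 10.3:

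- Base the maximum and minimum shift tables and the markedly abnormal table on all post-Baseline central-laboratory values in the relevant treatment period, including unscheduled and repeat values.
- Exempt these tables from the first-non-missing-value rule in SAP 3.1.
- Keep scheduled visits for the by-visit summaries, so that the two statements in the section agree.
- State that the Hy's Law count uses the same all-values source.
- State the period window. SAP 3.2.2 ends the Dose-Blind Period at the Week 48 visit, which leaves the end date open for subjects who stop early.

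Limiting the source to the central laboratory avoids mixing in local PDILI results, which Protocol 12.5.1 recognizes may differ from central ones.

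The cost is a few sentences of SAP text and a change in record selection for these tables; the data are already in the listings. The downside is that subjects tested more often have more chances to show an extreme value. A table footnote can say so.
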